patients in the caplacizuamb treatment group and 18 (9.8%) patients in the abciximab treatment group and were most frequently 'injury, poisoning and procedural complications' and 'cardiac disorders'. By Day 30 there was 1 death in the abciximab group and none in the caplacizumab group. After 1 year of FU, there were 5 deaths in each treatment arm. All but one of the deaths were considered to be unlikely/not related to the study drug. This other death (in the caplacizumab treatment group) was considered possibly related to treatment.

In this Phase II study, treatment-emergent antibodies were detected in 10.9% of the caplacizumab-treated subjects. No neutralizing antibodies were detected.

The PD assessments showed an immediate drop in RICO activity 5 to 10 minutes after the caplacizumab bolus injection. Clinically relevant RICO inhibition (< 20%) was maintained for 24 hours post-bolus in the caplacizumab group which was accompanied by an expected transient and mild decrease in vWF antigen and FVIII activity.

Phase III study

One Phase III study is currently ongoing in the development of caplacizumab for the treatment of acquired TTP:

Study ALX0681-C301 (HERCULES) is a randomized, double blind, placebo-controlled study to evaluate the efficacy and safety of caplacizumab treatment in addition to standard of care treatment (daily PE + corticosteroid treatment) in subjects with an acute episode of acquired TTP. The study will evaluate the efficacy of caplacizumab in more rapidly restoring normal platelet counts and the effect of treatment with caplacizumab on a composite endpoint of TTP-related mortality, prevention of recurrence of the presenting TTP episode and prevention of major thromboembolic events during study drug treatment.

After confirmation of study eligibility and after the start of PE treatment, approximately 92 subjects with a clinical diagnosis of acquired TTP are to be randomized in a ratio of 1:1 to either receive caplacizumab or placebo in addition to standard of care therapy. Subjects are treated for 30 days after stop of daily PE treatment (with a possibility of weekly extensions for a maximum of 4 weeks in case of persistent signs and symptoms of continued underlying disease activity) with a 4 week FU period. Subjects who experience a first exacerbation or a first relapse during treatment extension are to crossover to open-label caplacizumab.

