3.4. ASSESSMENTS

3.4.1. TIMING OF ASSESSMENTS

3.4.1.1. ELIGIBILITY PROCEDURES

Subjects who completed Study ALX0681-C301 will be given the option to participate in this FU Study ALX0681-C302 by signing a separate ICF, which will be obtained before any study-specific procedures are performed. The date of ICF signing will be recorded in the eCRF. After informed consent has been obtained, each subject will be assigned a unique subject ID number, which will be correlated/connected to their subject ID number in Study ALX0681-C301.

At the Final (28 day) FU visit in Study ALX0681-C301 or within one month thereafter, subjects will be screened according to the inclusion and exclusion criteria (section 3.2) and have other assessments performed as specified in the [Schedules of Assessments](#). For subjects for whom the Final (28 day) FU visit in Study ALX0681-C301 occurred prior to local approval and site activation for this study, a time window of +1 month after site activation is permitted to complete the screening/baseline visit.

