3.6.4. EVALUATION OF EFFICACY PARAMETERS

The following efficacy analyses will be performed:

- TTP-related events (defined as TTP-related death, recurrence of TTP or reported major thromboembolic event [e.g., myocardial infarction, cerebrovascular accident, pulmonary embolism or deep venous thrombosis]):
 - Summary of the (cumulative) proportion of subjects with TTP-related events over time (including after 12M FU visit, after 24M FU visit, and after 36M FU visit), as well as the number of such events.
 - Summary of the time to first TTP-related event (starting from screening/baseline visit), based on a Kaplan-Meier (KM) analysis.
- Mortality: mortality rate during the study.
- Recurrence of disease:
 - Summary of the (cumulative) proportion of subjects with recurrence of disease over time (including after 12M FU visit, after 24M FU visit, and after 36M FU visit), as well as the number of such events.
 - Summary of time to first recurrence (starting from end of previous TTP episode), based on a KM analysis.
 - Summary of TTP recurrence information, including duration of daily PE.
 - Descriptive analysis of incidence of recurrence in relation to ADAMTS13 levels after previous TTP episode.
- Reported major thromboembolic events (e.g., myocardial infarction, cerebrovascular accident, pulmonary embolism or deep venous thrombosis):
 - Summary of the (cumulative) proportion of subjects with reported major thromboembolic events over time (including after 12M FU visit, after 24M FU visit, and after 36M FU visit), as well as the number of such events.
 - Summary of the time to first reported major thromboembolic event (starting from screening/baseline visit), based on a KM analysis.
- Cognitive assessment:
 - Summary of RBANS cognitive assessment score, including change from baseline, over time.
 - Descriptive comparison of RBANS cognitive assessment score with reference population.
- Quality of life assessment:
 - Summary of HIT-6 scores, including change from baseline, over time.
 - Summary of SF-36 scales, including change from baseline, over time, and at the end of recurrence period.

All efficacy endpoints related to assessments on the Q6M FU visits will be analyzed using the ITO population. Summarization will be conducted on the total study population and by analysis group. For the group-wise analysis, the following groups will be considered:

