1.4 STUDY PLAN

This is a FU study for subjects who completed study ALX0681-C301 (HERCULES) according to the protocol (ie, completed the final [28 day] FU visit).

The study flow is depicted in [Figure 1](#).

Subjects who completed Study ALX0681-C301 will be given the option to participate in this FU study and attend twice yearly [Q6M] visits for 3 years starting with a baseline visit coinciding with or scheduled to take place within 1 month after the Final (28 day) FU visit in study ALX0681-C301. For subjects for whom the Final (28 day) FU visit in Study ALX0681-C301 occurred prior to local approval and site activation for this study, a time window of + 1 month after site activation is permitted to complete the screening/baseline visit. Assessments at these Q6M visits will include patient reported outcome measures, clinical assessments (including adverse events, safety laboratory parameters, vital signs and physical examination), and determination of anti-drug antibody [ADA], von Willebrand factor antigen [vWF:Ag] (PD parameter), and disease-related markers (a disintegrin-like and metalloprotease with thrombospondin repeats 13 [ADAMTS13] activity and Troponin I [TnI]).

Recurrence of TTP episode

[figure not shown]
Upon recurrence of TTP, defined as recurrent thrombocytopenia requiring initiation of daily plasma exchange [PE] (1), standard of care treatment consisting of daily PE and immunosuppression is to be initiated. In addition, an intravenous (i.v.) loading dose of open-label caplacizumab will be administered prior to initiation of daily PE followed by daily subcutaneous [s.c.] administration of caplacizumab for the duration of daily PE and for 30 days thereafter. Up to 1 PE (which may be spread over 2 or more sessions in 24 hours) may be given prior to initiation of treatment with caplacizumab as long as considered part of the PE for the treatment of the presenting TTP episode. Treatment with caplacizumab may be extended for a maximum of 4 weeks in case of persistent signs and symptoms of underlying disease activity (eg, ADAMTS13 activity profile remains below 10% based on weekly measurements).

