2.1.3.1.2 Duration of the TTP recurrence

The duration of TTP recurrence in days (time to platelet count response) is defined as initial platelet count $\geq 150 \times 10^9/L$ with subsequent stop of daily PE within 5 days. The start and end date time of the recurrence, for the calculation of the duration of TTP recurrence, are captured in the eCRF. There will be no imputation of missing data.

2.1.3.1.3 Outcome of the TTP recurrence:

The outcome of the TTP recurrence is assessed at the recurrence follow-up visit and is collected in the eCRF.

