2.1.3.5.5 Time to first recurrence of aTTP

The event of interest is the first recurrence of aTTP experienced by the patients in the ALX681-C302 study. Time to first recurrence (in days) is defined as the date from end of previous aTTP episode in the ALX0681-C301 study to the date of the event. Patients without an aTTP recurrence during the ALX0681-C302 study are censored at the end of the study. This endpoint is only computed for subjects who did not have any recurrence in the ALX0681-C301, or between the end of ALX0681-C301 trial and the beginning of the ALX-0681C302 trial.

2.1.3.5.6 Time to major thromboembolic events:

The time to the first major thromboembolic event (in days) is defined as the date from screening/baseline visit to the date of the first thromboembolic event. Patient without a thromboembolic event are censored at the end of the study.

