2.4.4.3 Recurrence of TTP

The number and percentage of participants with a recurrence of TTP as well as the number of such events, will be summarized over time for the ITO population (after 12M FU, 24M FU and 36M FU).

Time to the first recurrence of TTP will be summarized on the ITO population, using Kaplan-Meier (KM) estimates such as the median, 25% percentile and 75% percentile with associated 95% CIs, as well as the number of events and the number of censored observations. The KM estimates will also be presented graphically.

A subgroup analysis of incidence of recurrence of TTP to ADAMTS13 levels ($\geq 10\%$, $< 10\%$) after end of previous TTP episode in the ALX0681-C301 trial will be performed on the ITO population.

2.4.4.4 TTP recurrence information.

TTP recurrence information will be summarized for the recurrence population.

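### Time to first recurrence: the clock starts before C302 entry but plain Kaplan-Meier uses no entry time, so recurrence is too low in expectation when entry gaps differ; the size depends on late entry

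*SAP*

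**What the plan says.** - **Origin and event.** SAP 2.1.3.5.5: "Time to first recurrence (in days) is defined as the date from end of previous aTTP episode in the ALX0681-C301 study". The event is the first recurrence in C302. Protocol 3.6.4 has the same origin: "Summary of time to first recurrence (starting from end of previous TTP episode), based on a KM analysis".
- **Who is included.** SAP 2.1.3.5.5: "This endpoint is only computed for subjects who did not have any recurrence in the ALX0681-C301, or between the end of ALX0681-C301 trial" and the start of C302.
- **Estimator.** SAP 2.4.4.3: "Time to the first recurrence of TTP will be summarized on the ITO population, using Kaplan-Meier (KM) estimates such as the median, 25% percentile", together with the 75th percentile, 95% confidence intervals and a plot. Neither document mentions an entry time, left truncation or a landmark.
- **Entry, standard route.** SAP 1.4: "a baseline visit coinciding with or scheduled to take place within 1 month after the Final (28 day) FU visit in study ALX0681-C301".
- **Entry, late route.** If the final C301 visit came before local approval and site activation, Protocol 3.4.1.1 says: "a time window of +1 month after site activation is permitted to complete the screening/baseline visit". No limit is counted from the C301 visit.
- **C301 treatment.** Protocol 1.2.4 describes 30 days of drug after daily plasma exchange (PE) stops, "with a possibility of weekly extensions for a maximum of 4 weeks in case of persistent signs and symptoms of continued underlying disease activity".
- **Acknowledgement.** Protocol 3.6.4 and SAP 2.4.4 both recognise that baseline timing varies. They leave sensitivity analyses optional, and the SAP specifies none.

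**The concern.** A patient enters this analysis only by reaching C302 without a recurrence. From the end of the C301 episode to C302 baseline that patient cannot contribute an event, yet plain KM keeps the patient in the risk set from time zero. When other patients have already entered and are having events, the denominators are too large and the curve rises too slowly.

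Time to recurrence is among the main endpoints in the protocol synopsis, and describing it is the purpose of the analysis. The KM curve and its quartiles would be the affected outputs.

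The origin also lacks a date. SAP 2.1.3.1.2 says "The duration of TTP recurrence in days (time to platelet count response) is defined as initial platelet count" reaches the threshold with daily PE then stopped. SAP 2.4.4.9.1 instead uses the end of treatment of the last C301 episode. The first defines the duration of a recurrence and the second a subgroup; neither defines this endpoint. The choice shifts time zero by at least 30 days.

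**Working it through.** The plan states no expected recurrence figure for this endpoint, so there is none to reproduce.

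**Direction.** At each event time both estimators see the same number of events, d. The plain risk set contains everyone in the delayed-entry risk set plus patients not yet entered, so n(plain) ≥ n(delayed) and 1 − d/n(plain) ≥ 1 − d/n(delayed). Multiplying over event times, plain KM recurrence cannot exceed delayed-entry KM recurrence. If no event precedes the last entry, the two are identical.

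**Inputs from the documents.** Earliest entry is day 28 if the episode ends with C301 treatment (28-day follow-up), or day 30 + 28 = 58 if it ends with daily PE. Standard-route spread is 0 to 1 month. Follow-up is 36 months from entry.

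**Assumptions.** First-year hazard 0.10, 0.25 or 0.40 per year, then 0.10 per year; gaps uniform; late entrants as shown; no dropout before month 12; entry time independent of risk.

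**Formulas.** Let S be the recurrence-free probability from the origin and g the gap. Patients are kept only if T > g.
- Target, conditional on being recurrence-free at the earliest entry: 1 − S(t)/S(g_min). Delayed-entry KM estimates this.
- Plain KM: 1 − E[S(max(t, g))]/E[S(g)].

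**Example: 0.25 per year, earliest entry day 28, spread 0 to 30 days (mean gap 43 days).**
- Target: 1 − exp(−0.25 × 337/365) = 20.6%.
- Plain KM: 1 − exp(−0.25 × 322/365) = 19.8%.

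**12-month risk, earliest entry day 28** (shortfall in points, from unrounded values):

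| First-year hazard | Target | Plain KM, spread only | Spread, 30% late to month 12 | Spread, 50% late to month 18 |
|---|---|---|---|---|
| 0.10 | 8.8% | 8.4% (0.4) | 7.3% (1.5) | 5.8% (3.0) |
| 0.25 | 20.6% | 19.8% (0.8) | 17.4% (3.2) | 14.1% (6.5) |
| 0.40 | 30.9% | 29.7% (1.1) | 26.4% (4.5) | 21.9% (9.0) |

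With earliest entry at day 58 the spread alone costs 0.4, 0.8 and 1.2 points. Simulations under the same assumptions agree, with spread-only shortfalls from 0.3 points. With equal gaps the shortfall from the target is zero.

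**25th percentile, 0.25 per year, day 28.** The cumulative hazard needed is −ln 0.75 = 0.2877. The target accrues 0.2308 by month 12, and the remaining 0.0569 takes 0.0569/0.10 × 12 = 6.8 months, giving 18.8 months. Plain KM reads about 20 months with the spread alone and about 24 with 30% late to month 12. The median is not reached within 36 months.

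**A second model** (Weibull shape 0.6, 36% recurrence at 36 months, large samples). Gaps of 0.92 to 1.92 months: 12-month plain KM 15.4%, delayed entry 16.6%. Half the patients entering at 2 to 3 months and half at 2 to 9: 10.9% against 14.0%.

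**Single trials.** With the standard-route spread only, the two 12-month estimates were identical in 21% to 86% of simulated small trials. The SD of plain KM at 12 months was 3.5 to 6.3 points (assumed N of 92 to 40, 0.25 per year).

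**The case against.** The strongest reply concerns size. On the standard route, the only one whose spread is documented, the bias is under about 1.2 points against an SD of several points, and in many datasets it would be nil. Delayed entry costs early precision. In 27 simulated settings (hazards 0.10 to 0.40 per year, N of 40, 70 or 92, and 0%, 10% or 30% late to month 4), plain KM had the lower 12-month root mean squared error (RMSE) in every one. At 0.25 per year with no late entry it was 6.2 against 7.2 at N = 40 and 4.2 against 4.6 at N = 92. If the delayed-entry curve starts only once 10 patients have entered, the comparison narrows to 6.2 against 6.4 and 4.2 against 4.4. Delayed entry with the start rule gains clearly from about 30% late to month 12, at 0.25 to 0.40 per year.

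The rest is also fair. The study is descriptive with no formal test. The 12-, 24- and 36-month recurrence counts do not use this clock, and time to first TTP-related event, which includes recurrence, has its own KM from baseline. The protocol says risk seems highest in the first year, but its Phase II account puts 7 of 8 first-month relapses 4 to 10 days after stopping drug. Relapses that early fall before C302 entry and are excluded under either estimator.

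All of this stands as a limit on materiality. It does not rescue the estimator: the bias has one direction, does not shrink with more patients, and depends on a gap distribution that the sponsor can tabulate but the plan never asks for.

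**Conclusion.** The point holds in a limited form. As written, the analysis counts event-free time by construction as time at risk. Plain KM is then never above delayed-entry KM and is too low in expectation if gaps differ and some risk exists between the earliest and latest entry. Direction is certain. Size rests on assumed hazards and gaps: about 0.3 to 1.2 points at 12 months from the standard-route spread, and several points only if late entry was common.

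Stronger readings that a reader might infer are not supported:
- **That recurrence is understated in every dataset with unequal gaps.** The curves coincide if no event precedes the last entry.
- **That the loss is 6 to 9 points.** This needs about half the patients entering late, up to month 18, with a first-year hazard of 0.25 to 0.40 per year. The documents permit late entry but give neither its frequency nor its length.
- **That the contrast between former C301 groups is distorted.** That would need gaps that differ by group, which the documents do not show.
- **That delayed entry recovers all risk from the origin.** It cannot recover risk before the earliest entry.

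The undefined origin is a one-line clarification. The change should be made, because time to recurrence is a main endpoint and the correction needs no new data.

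**What to change.** 1. In SAP 2.1.3.5.5, keep the protocol's origin and state which date ends the previous episode for patients without a C301 recurrence.
2. Report the distribution of the gap from that date to C302 baseline, overall and by C301 group.
3. In SAP 2.4.4.3, use left-truncated KM with entry at the C302 screening/baseline visit, starting the curve once a pre-stated number of patients (for example 10) have entered.
4. Label the curve as conditional on being recurrence-free at entry and as assuming that entry time is independent of recurrence risk.
5. Show plain KM only as a labelled comparison.
6. State that censoring is at each subject's own last visit or termination date. The note after Table 3 in SAP 2.5.4 already points that way.

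A clock starting at C302 baseline is not an equivalent substitute: it mixes patients at different times since the episode and departs from protocol 3.6.4.

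**Cost.** SAP wording, a gap table and an entry-time option in standard software. Early precision falls somewhat: with the start rule, 12-month RMSE can be up to about 0.5 points higher when late entry is rare. Without such a rule, one very early event can drive the curve to 100% (0 to 6 of 3,000 simulated trials). If entry time is related to risk, delayed entry is also biased, though less. With C301 extension in 15% to 30% of patients at 1.5 to 3 times the hazard, it was 0.1 to 0.9 points low, against 1.1 to 2.0 for plain KM.

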(1) caplacizumab-treated, defined as subjects in the ITO population who have been randomized to caplacizumab in Study ALX0681-C301, evaluated up to their first recurrence⁺⁺⁺; (2) standard of care-treated, defined as subjects in the ITO population who have been randomized to placebo in Study ALX0681-C301, evaluated up to their first recurrence.

All efficacy endpoints related to assessments during the recurrence period will be analyzed using the recurrence population. The effect of retreatment of caplacizumab on these endpoints will be evaluated.

Select sensitivity analyses may be planned to assess the effect of heterogeneity in the timings of the baseline visit between subjects. More details will be provided in the SAP. Unless specified otherwise, no missing data imputation will be applied, and all efficacy endpoints will be analyzed as observed.

3.6.5. EVALUATION OF PHARMACOKINETIC AND PHARMACODYNAMIC, DISEASE RELATED MARKERS AND IMMUNOGENICITY PARAMETERS

Individual study drug concentrations will be listed. In addition a listing of the actual sampling times relative to the study drug administration times will be presented.

Drug concentrations will be summarized by sampling time using descriptive statistics and will be listed and summarized in tabular and/or graphical form.

All PD and disease-related marker data will be summarized using descriptive statistics and will be listed and summarized in tabular and/or graphical form.

Immunogenicity will be assessed through listing of individual (ADA, mADA and nAb) results by subject, summary tables and immunogenicity time profiles. Immunogenicity data will be correlated with PK and PD readout using descriptive statistics per subject category based on pre-Ab and TE ADA status (using ADA results obtained in Study ALX0681-C301), summarized in tabular and/or graphical form. In addition, immunogenicity will be correlated with possible safety findings. The effect of retreatment with caplacizumab on immunogenicity will be assessed.

⁺⁺⁺ Subjects who had a recurrence during Study ALX0681-C301 or between the Final (28 day) FU visit in Study ALX0681-C301 and Screening/Baseline in Study ALX0681-C302, will not be considered for the group-wise analyses.

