2.3 ANALYSIS POPULATIONS

2.3.1 Intention-to Observe (ITO) Population

All subjects who enrolled in study ALX0681-C302. Unless otherwise specified, the ITO population will be used for the analysis of the Q6M FU data on efficacy, disease-related markers, PD, immunogenicity and safety.

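### The SAP removes subjects with an earlier recurrence from the whole time-to-first-recurrence endpoint, so the total-population Kaplan-Meier curve is not the ITO estimate it is labelled as

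*SAP*

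**What the plan says.** **Protocol 3.6.4** plans this analysis: "Summary of time to first recurrence (starting from end of previous TTP episode), based on a KM analysis". Its closing text sets two levels of reporting: "Summarization will be conducted on the total study population and by analysis group". A footnote to the group definitions deals with subjects who had a recurrence during C301, or between the final C301 follow-up visit and C302 screening/baseline. These subjects "will not be considered for the group-wise analyses". Nothing removes them from the total-population summary.

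**SAP 2.4.4** repeats both elements with the same scope: total population and by group, with the exclusion attached to the group-wise part.

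**SAP 2.4.4.3** states: "Time to the first recurrence of TTP will be summarized on the ITO population, using Kaplan-Meier (KM) estimates". **SAP 2.3.1** defines that population as "All subjects who enrolled in study ALX0681-C302", without any condition on recurrence history.

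**SAP 2.1.3.5.5**, which defines the endpoint, ends differently: "This endpoint is only computed for subjects who did not have any recurrence in the ALX0681-C301". A second limb applies the same restriction to recurrences in the interval separating the two studies. Neither limb mentions the group-wise analysis.

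**SAP 1.6**, the list of statistical modifications, contains one item: the refractory-disease endpoint is not calculated.

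**The concern.** Time to recurrence is among the main endpoints in the protocol synopsis, and describing the long-term impact of TTP is one of the three study objectives. The total-population curve is the single estimate that addresses that objective for everyone followed. If the endpoint does not exist for subjects with an earlier recurrence, the curve describes a subset selected on disease history while carrying an ITO label.

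Two practical consequences follow. The same SAP section counts subjects with a recurrence at 12, 24 and 36 months on the full ITO population, so the event total under the KM curve need not agree with the count beside it. Also, the restriction sits in an endpoint definition and is not among the declared modifications, so a reader of the tables could miss that the population has changed.

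**Working it through.** **Comparison of the texts.** The plan states no sample size, event count or recurrence rate for this endpoint, so there is no figure to reproduce. The check is whether the passages can all be followed for the total-population curve.

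| Place | Subjects with a C301 or inter-study recurrence |
|---|---|
| Protocol 3.6.4, endpoint and reporting levels | Included in the total; no exclusion stated |
| Protocol 3.6.4, footnote | Out of the group-wise analyses only |
| SAP 2.4.4 | Out of the group-wise analyses only |
| SAP 2.4.4.3 with 2.3.1 | Included (ITO, all enrolled) |
| SAP 2.1.3.5.5 | Endpoint not computed for them at all |
| SAP 1.6 | No change declared |

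The fifth row cannot be reconciled with the first four for the total curve. A programmer who follows the endpoint definition produces a restricted curve; one who follows 2.4.4 and 2.4.4.3 produces an ITO curve.

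**What is not affected.** Three other outputs carry no such exclusion: the number and percentage with a recurrence at 12, 24 and 36 months (SAP 2.4.4.3), the KM for first TTP-related event, which includes recurrence and runs from C302 baseline (SAP 2.1.3.5.2 and 2.4.4.1), and recurrence incidence by number of C301 recurrences (SAP 2.4.4.9.1).

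**Count mismatch.** Subjects with a recurrence (full ITO) − events in the restricted KM = excluded subjects who recur in C302. This is zero only if none of them does.

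**Illustration of direction and size.** Let r0 be the cumulative risk in the retained subjects, f the share excluded, and HR the hazard of excluded relative to retained subjects. Under proportional hazards:

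- full-ITO risk = (1 − f) × r0 + f × [1 − (1 − r0)^HR]
- full-ITO risk − r0 = f × [(1 − r0) − (1 − r0)^HR]

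The second line shows that the sign depends only on whether HR is above or below 1; f only scales it.

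All three inputs are assumptions:

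- r0 = 18%, borrowed for scale from the literature median in Protocol 1.1 (reported range 3% to 84%). It is not a C302 rate.
- f = 10% to 35%. The upper end is guided by Phase II (Protocol 1.2.4), where 13/36 and 13/39 subjects had an exacerbation and/or relapse: 26/75 = 34.7%. No C301 figure is given.
- HR = 0.5 to 3, with no source in the documents.

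Worked case: r0 = 0.18, f = 0.35, HR = 2 gives 0.35 × (0.82 − 0.82²) = 0.35 × (0.82 − 0.6724) = 0.052, so the full-ITO risk is 23.2% against 18.0% on the restricted curve.

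| f | HR 0.5 | HR 1 | HR 2 | HR 3 |
|---|---|---|---|---|
| 10% | 17.1% | 18.0% | 19.5% | 20.7% |
| 20% | 16.3% | 18.0% | 21.0% | 23.4% |
| 35% | 15.0% | 18.0% | 23.2% | 27.4% |

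Against these values the restricted curve always reads 18.0%: from 9.4 points too low to 3.0 points too high. With r0 at 10% or 30% the sign pattern is the same; at HR 2 the curve is 0.9 to 3.1 or 2.1 to 7.4 points too low.

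**The case against.** A reader might infer that the curve understates recurrence risk as a matter of fact, because the subjects removed have already shown unstable disease. The documents do not support that. Protocol 1.2.4 and 1.2.5 link relapse soon after stopping the drug to persistently low ADAMTS13 activity, which makes a higher later hazard plausible. No passage gives a later recurrence rate by C301 recurrence history, however. Enrolled subjects had all completed C301 follow-up, and those who recurred may have received intensified immunosuppression. A size calculation that uses only hazard ratios above 1 builds understatement into its assumptions.

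The other side has further good arguments. Total-population recurrence is still visible in the unrestricted counts, the composite KM and the incidence subgroups, so one curve is affected and not the whole recurrence assessment. The study is descriptive, with no formal tests (SAP 2.4.4.8) and no statistical sample size (SAP 1.3). The restriction is written openly in the endpoint definition, and because SAP 2.4.4 keeps the narrower scope, this may be a drafting slip and not a decision.

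These arguments limit the consequence but do not remove the conflict. If it is a slip, the wording still directs a programmer to the wrong population.

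The exclusion might also be defended as securing a clean time origin. That is weak for C301 recurrences: the protocol's origin is the end of the previous episode, and SAP 2.4.4.9.1 already refers to the end of treatment of the last C301 recurrence episode. It has more force for inter-study recurrences. Protocol 3.4.2 collects TTP episodes as medical history but does not say that end dates are recorded.

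**Conclusion.** Wrong as written. SAP 2.1.3.5.5 extends a group-wise exclusion to an entire main endpoint, against Protocol 3.6.4 and against SAP 2.4.4 and 2.4.4.3, without declaring it in SAP 1.6. That conclusion rests on the text alone and needs no assumption about risk. The total-population KM would not be an ITO estimate.

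Any effect on the estimated risk is conditional: too low if subjects with earlier recurrences recur more often, unbiased if their hazard is the same, too high if it is lower. The sizes shown are illustrative, assume proportional hazards, and should not be read as an estimated bias. This should be corrected, but it is confined to one descriptive curve.

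**What to change.** Reword the last sentence of SAP 2.1.3.5.5 so that it applies to the group-wise KM only, matching the protocol footnote and SAP 2.4.4.

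For the total-population KM, include every ITO subject. Start the clock at the end of the most recent TTP episode before C302 baseline: the last C301 episode or, where there was an inter-study recurrence, that episode as recorded in the TTP history.

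If no origin date can be obtained for some subjects, report how many are left out, relabel the analysis set so that it is not called ITO, and declare the change in SAP 1.6.

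The cost is SAP wording, derivation of origin dates for the re-included subjects, and one additional KM run. C301 dates should be straightforward; inter-study dates may need a look at the history records. An origin before C302 entry raises delayed entry under either definition; that is a separate question which this change neither creates nor settles.
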